5.6 Clinical Study Supplies at the Clinical Study Site

5.6.1 Investigational Study Drug and ADPs

Lucinactant and ADPs will either be shipped directly to the investigational clinical study site pharmacies or to a designated location at the clinical study sites. A Clinical Supply Receipt Form will accompany the shipment. Study sites must verify each shipment via the Clinical Supply Receipt Form and study IWRS, and report study drug shipping temperatures to Discovery as outlined in the study manual.

5.6.2 Ancillary Supplies

Ancillary supplies (eg, CPAP system, nasal prongs, high pressure hoses) will be shipped directly to the investigational clinical study site NICU or to a designated location at the clinical study site. A Clinical Supply Receipt Form will accompany the shipment. Study sites must verify each shipment to Discovery via the Clinical Supply Receipt Form.

5.6.3 Dispensing

Study supplies (study drug, ADP, and related study equipment) will be dispensed in accordance with the subject's randomized dosing group (Section 5.2.2). The NICU pharmacist or designated study personal will provide on-site storage, dispensing, reconciliation, and documentation of study supplies as outlined in the study manual. Study drug and ADP components (ie, ADP

syringe and heater assembly) must be fully reconciled at the end of the study. The study clinical site monitor will provide oversight of these tasks and communicate any significant findings or indications of noncompliance to Discovery.

5.6.4 Storage of Lucinactant and Aerosurf Delivery System

Lucinactant must be stored in a secured area of the hospital pharmacy or NICU at 2°C to 8°C and protected from light until use. Study sites must monitor and log storage temperatures. All temperature excursions should be reported to Discovery as outlined in the study manual.

The ACU and ADPs will be delivered separately and must also be stored in a secure location under the recommended storage conditions outlined in the ADS Operator's Manual.

5.7 Study Compliance

Study compliance will be based on the actual delivery time of lucinactant for inhalation in comparison to the subject's randomized aerosolization time. Aerosolization time will be tracked by the ACU, which will display a continual count of lucinactant exposure time throughout the aerosol delivery period. The length of lucinactant exposure time (as observed through aerosol delivery and ACU display) will be documented in the study eCRF. The ACU will also display an interface to allow for emergent aerosol discontinuation. PIs are to discontinue aerosol delivery if a potential safety risk to the subject is identified at any point during the aerosol delivery period.

The number of subjects randomized but not treated, and the number of subjects prematurely discontinued from aerosol delivery will be recorded in the eCRF and summarized in the study report.

No diaries will be required since lucinactant for inhalation will be administered at the clinical site.

5.8 Study Drug and Device Accountability

It is the responsibility of the PI and trained designee to ensure that all study supplies (vials of lucinactant for inhalation, all components of the ADS, and related equipment) are inventoried, and appropriately stored, in accordance with study guidance documents (eg, study protocol, ACU Operator's Manual), and used only for study subjects, by study trained staff.

5.8.1 Study Supply Accountability

The following guidelines must be followed to ensure the storage and accountability of the study supplies is consistent with the study protocol:

1. Used or partially used vials of lucinactant for inhalation and ADPs must be kept separate from unused supplies throughout the life of the study.
2. Designated study personnel will return all unused study drug vials and ADPs to the pharmacy or the clinical supply storage area immediately after the completion study aerosol delivery.
3. Reconciliation of study supplies will be performed at each study visit by the clinical site monitor and recorded appropriately in the pharmacy log and drug and device accountability records.
4. Storage conditions, as described in the study manual, will be assessed and documented by the clinical site monitor at each study visit (ensuring all supplies are kept in a secure area with restricted access).
5. Dispensing information must be recorded in the inventory log and kept with the study site records throughout the study.
6. Designated study personnel (eg, pharmacists) will not supply study drug, ADPs, and ancillary supplies to any person other than designated study staff.
7. Study sites will not dispense the study supplies to any sites other than those listed on Form FDA 1572, Statement of Investigators.

6 SAFETY REVIEW COMMITTEE

The purpose of the SRC is to evaluate the degree of risk involved in study subject participation within each dosing group to determine if study continuation in accordance with the current protocol holds the potential to institute any undue harm, or threat to the safety and welfare of study subjects. Safety and tolerability data will be assessed at the time all active subjects in each dose group completes assessments and procedures through 72 hours.

The SRC will consist of 3 to 5 experts in the field of RDS; at least 2 of the experts must be neonatologists.

6.1 Safety Reviews

The SRC reviews will consist of the evaluation of (1) all AEs (2) ADEs relevant to potential subject safety issues (3) case reviews of subjects with reported SAEs and (4) summary tables of all safety endpoints (Section 3.3).

Following a thorough independent review of available study data, the SRC will provide timely recommendations to the Discovery study team. Recommendations may consist of, but not be limited to the following:

- Continue enrollment at the next higher dose level, which includes a potential repeat dose,
- Suspend or close study enrollment

At each review, the control subjects will be summarized in aggregate.

An independent statistician, not a member of the committee, will be responsible for the statistical analysis of the data to be reviewed at each meeting.

6.2 Safety Enrollment Holds

Failed tolerability will be established based on analysis of AEs. In particular, AEs related to the administration of lucinactant for inhalation are of particular interest. To prevent undue risk to subjects, if more than 2 subjects per dosing group experience an SAE related to dosing, enrollment and dosing will be suspended and further enrollment and dosing will proceed only if and when the SRC deems it to be appropriate.

In addition, if a treated subject dies during the first 12 hours following and related to lucinactant for inhalation administration, then an unscheduled meeting of the SRC will be called. Safety and

tolerability data will be presented to the SRC for their immediate review. Study enrollment will be suspended until such time that a safety assessment has been completed. Enrollment and dosing will proceed only if and when the SRC deems it to be appropriate. If the SRC deems it to be appropriate to re-initiate enrollment after an enrollment hold, IRB approvals will be obtained before the re-initiation of subject screening and enrollment activities.

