- In the PI's best medical judgment, initiating or continuing the subject's exposure to lucinactant for inhalation is not in the best interest of the subject's safety, such as hemodynamic instability.
- Signs of acute respiratory deterioration as evidenced by an increased respiratory rate or an observed increase in respiratory effort (work of breathing) plus at least one of the following:
 - a) An FiO₂ ≥ 0.70 or a sustained (≥ 10 minutes) increase from baseline by ≥ 0.30 to maintain adequate oxyhemoglobin saturation (SpO₂ $\geq 88\%$),
 - b) A PCO₂ > 70 mm Hg or a progressive increase from baseline to ≥ 20 mm Hg above baseline and confirmed with a blood gas,
 - c) Recurring episodes of bradycardia defined as a heart rate < 100 bpm for ≥ 20 seconds,
 - d) A sustained apneic event, defined as apnea for at least 20

seconds in duration and meeting at least one of the following: (1) HR < 100 bpm, (2) desaturation (oxygen saturation < 80%), (3) requirement for IPP breaths using inflating pressures above the set CPAP pressure administered manually or mechanically through any patient interface.

Enrollment hold criteria:

The study will be placed on enrollment hold until further evaluation by the SRC if one of the following criteria are met:

- If > 2 subjects per dosing group experience a SAE related to lucinactant for inhalation administration
- If ≥ 1 subject dies during first 12 hours following and related to lucinactant for inhalation administration

Statistical Analysis: The statistical analysis of both the primary and secondary safety and tolerability objectives will be based on all randomized preterm neonates in the study. In addition, data from all evaluable preterm neonates will be analyzed for efficacy signals as an exploratory endpoint. No hypothesis testing or statistical comparisons will be performed.

Interim Analyses: All available safety endpoint data captured from randomization to completion of 72 hours for active subjects, and all available safety endpoint data for control subjects, will be evaluated by the SRC. As this is an open-label study with no hypothesis testing, no adjustments for *p*-values are required or employed for the interim analyses.

TABLE OF CONTENTS

TITLE PAGE	1
AEROSURF PROTOCOL SUMMARY	3
TABLE OF CONTENTS	15
LIST OF ABBREVIATIONS	20
1 INTRODUCTION.....	22
1.1 Treatment of Neonatal Respiratory Distress Syndrome	22
1.1.1 Continuous Positive Airway Pressure in Neonatal Respiratory Distress Syndrome	23

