5.2.4 Sequential Dosing Scheme

The study dosing will initiate in Dosing Group I (the lowest dose), and continue to Dosing Group II after completion of enrollment. Each dosing group will enroll sequentially following completed enrollment of the previous dosing group. After all active subjects within each dosing group have completed 72 hours, the SRC will review the safety and tolerability of this dose.

If there appears to be intolerability with a given dose or operational challenges administering a dose, the remaining subjects may have the dose decreased to a previously administered dose, after consultation with the SRC.

Further details on the dosing for each dosing group are provided in Section 5.2.2.

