9.1.4 Serious Adverse Events

A SAE is any untoward medical occurrence that, at any dose meets one of the following criteria (ICH E2A, *Clinical Safety Data Management: Definitions and Standards for Expedited Reporting*):

1. Results in death
2. Is life-threatening
3. Requires inpatient hospitalization or prolongation of existing hospitalization
4. Results in persistent or significant disability/incapacity
5. Is a congenital anomaly/birth defect
6. May be considered serious when based upon appropriate medical judgment

When the investigator-trained designee becomes aware of an SAE, Discovery must be notified as soon as possible (and no later than 24 hours after the event has occurred) by telephone, regardless of the relationship (or lack thereof) of the SAE to study participation.

SAEs should be reported to Discovery's reporting line (see Section 9.2).

When reporting SAEs, the following information should be provided:

- | | |
|-------------------------------|---|
| 1. Study identifier | 7. Clarification on whether study aerosol was discontinued |
| 2. Study center | 8. The reason why the event is classified as serious |
| 3. Subject number | 9. The Investigator's assessment of the association between the event and study participation |
| 4. A description of the event | |
| 5. Date of onset | |
| 6. Current status | |

All reports of SAEs must be followed up within 24 hours (or sooner at the request of the medical monitor) by the completion of the SAE form and signature by the person who completed the form and the PI. This should be emailed to the local clinical site monitor or faxed to Discovery at [contact] (USA).

In accordance with Discovery's standard operating procedures (SOPs) and regulatory agency (eg, FDA) regulations, investigators will be notified of the occurrence of serious, unexpected, related AEs. The PI must promptly inform the relevant IRB/IEC in accordance with ICH E6 of all AEs that are deemed related to study participation (ie, there is a reasonable possibility that the AE may have been caused by the drug or device) and are thus deemed a significant new AE or risks with respect to the drug or device.

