12.1 Institutional Review Board

The protocol, including any amendments and the ICF, will be submitted to an IRB at each investigational site for approval to conduct the study. Before the initiation of the study at each investigational site, a designee at the site will forward to Discovery a copy of the site’s local IRB approval to conduct study the study. This approval must refer to the study by exact protocol title and number and should identify the documents reviewed and the date of review.

Protocol and ICF modifications or changes may not be initiated without prior written IRB approval, except when necessary to eliminate immediate hazards to the study subjects or when the change(s) involves only logistical or administrative aspects of the study. Such modifications will be submitted to the IRB and written verification that the modification was submitted and subsequently approved should be obtained. A site must receive approval from Discovery on any ICF modification before submission to the IRB for approval and subsequent implementation at the study site. Protocol modifications (ie, amendments) may only be enacted by Discovery.

The IRB must be informed of revisions to other study-related documents or study information that was originally submitted for review. Revised study documentation and related informational updates may include but are not limited to the following:

1. Serious and/or unexpected AEs occurring during the study (reported in accordance with the SOPs and policies of the IRB)
2. Any new study information that may adversely affect subject safety or study conduct
3. Annual study updates or IRB requests for reassessment of the study
4. Timely communication of significant actions and related findings from the SRC (to include study enrollment holds or expansion, protocol amendments, or early study closure).
5. Notification of major study/site milestones to include study/site closure

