7.2 INTERIM ANALYSES

Four interim analyses are planned. Each interim analysis will occur when all subjects from each dosing group have been enrolled and all active subjects have completed 72 hours. In addition to the planned analyses, if more than 2 subjects in any dosing group experience an SAE related to dosing, aerosol delivery will be suspended and further dosing will proceed only if and when the SRC deems it to be appropriate.

In addition, if a treated subject dies due to a related event during or within 12 hours after aerosol administration, then an unscheduled meeting of the SRC will be called. Safety and tolerability data will be presented to the SRC for their immediate review. Study enrollment will be suspended until such time that a safety assessment has been completed and dosing will proceed only if and when the SRC deems it to be appropriate. If the SRC deems it to be appropriate to re-initiate enrollment after an enrollment hold, local IRB approvals will be obtained before the re-initiation of subject screening and enrollment activities. The objective of the interim analyses is to ensure the safety of subjects at a particular dose before proceeding to the next higher dose.

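### A related death more than 12 hours after dosing triggers no automatic unscheduled SRC meeting or hold; toward an automatic hold it counts only as one of the more than 2 related-SAE subjects needed in that dosing group

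*Protocol*

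**What the plan says.** The single-death trigger appears in three places, and all three agree.

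- Protocol Section 6.2: "if a treated subject dies during the first 12 hours following and related to lucinactant for inhalation administration", an unscheduled SRC meeting is called and enrollment is suspended until the safety assessment is done.
- Protocol summary, enrollment hold criteria: "If ≥ 1 subject dies during first 12 hours following and related to lucinactant for inhalation administration".
- SAP Section 7.2: "if a treated subject dies due to a related event during or within 12 hours after aerosol administration".

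The other automatic trigger, also in Section 6.2, suspends enrollment and dosing "if more than 2 subjects per dosing group experience an SAE related to dosing".

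Apart from these triggers, the SRC meets on a schedule. Section 6 states: "Safety and tolerability data will be assessed at the time all active subjects in each dose group completes assessments and procedures through 72 hours". Section 5.2.4 says the same: "After all active subjects within each dosing group have completed 72 hours, the SRC will review the safety and tolerability of this dose". Under Section 6.1 each review includes case reviews of subjects with SAEs, and the SRC may recommend suspending or closing enrollment.

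A death is an SAE (Section 9.1.4). It goes to the sponsor by telephone within 24 hours, and the investigator must promptly tell the IRB of related events. The same section says "investigators will be notified of the occurrence of serious, unexpected, related AEs". Section 12.1 lists "Serious and/or unexpected AEs occurring during the study" among the matters sent to the IRB.

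**The concern.** A related death at 11 hours requires immediate review by the independent committee. The same death at 13 hours does not. The plan gives no reason for placing the cut at 12 hours, although its scheduled SRC review covers 72 hours, its late respiratory worsening category runs to 7 days after birth, and adverse events are followed to the final visit.

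Section 9.1.4 names the sponsor, investigators and IRBs as recipients of SAE information. No visible text sends an SAE to the SRC between scheduled reviews. Whether the committee sees a late related death before the next infant is dosed therefore depends on someone choosing to tell it.

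Repeat dosing adds an ambiguity. A repeat dose may be given 2 to 24 hours after the first, and the rule does not say which administration starts the 12-hour clock.

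**Working it through.** The plan states no operating characteristic for its hold rules, and Section 13.3 says sample size is not based on statistical estimation, so there is no figure to reproduce. The check has two parts: what the rules force, and how long the scheduled review can take.

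**1. What the rules force.** A late related death fails the time condition of the death trigger. As a related SAE it adds one subject to the other rule, which needs more than 2, that is at least 3, in one dosing group. With 8 active infants per group, up to 2 of 8 (25%) could have late related deaths with no forced hold, provided no third infant in that group has a related SAE.

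**2. How likely the SAE rule is to step in.** After one late related death, at least 2 of the other 7 active infants must have a related SAE. If each has an independent risk q, the probability is 1 − (1−q)^7 − 7q(1−q)^6. The documents give no value for q, so a range is assumed:

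- q = 5%: 1 − 0.698 − 0.257 = 4.4% (unrounded terms)
- q = 10%: 1 − 0.478 − 0.372 = 15.0%
- q = 20%: 1 − 0.210 − 0.367 = 42.3%

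**3. Time to the scheduled review.** Inputs: 8 active and 8 control infants per group (Section 5.2.2), 1 subject per site per 4 weeks at about 12 sites, and recruitment over 7 months (Section 2.3).

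- At 12 sites: 12 ÷ 4 ÷ 2 = 1.5 active infants per week. This rate fills 64 places in 64 ÷ 3 = 21.3 weeks, faster than the planned 7 months.
- At 64 infants over 7 months (30.4 weeks): 64 ÷ 30.4 ÷ 2 = 1.05 active infants per week.

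Wait from dose to review = (active infants still to be dosed ÷ weekly rate) + 3/7 week.

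| Position of the infant in the group | Further active infants | 12 sites | 64 in 7 months |
|---|---|---|---|
| First | 7 | 4.67 + 0.43 = 5.1 weeks | 6.65 + 0.43 = 7.1 weeks |
| Fourth | 4 | 2.67 + 0.43 = 3.1 weeks | 3.80 + 0.43 = 4.2 weeks |
| Eighth | 0 | 0.43 week (3 days) | 0.43 week (3 days) |
| Mean of positions 1 to 8 | 3.5 | 2.33 + 0.43 = 2.8 weeks | 3.33 + 0.43 = 3.8 weeks |

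These waits assume that the SRC meets as soon as the last active infant reaches 72 hours. Counted from the death, each is shorter by the time from dose to death. Section 4.1 gives about 25 sites. At the same per-site rate they would fill the trial in 64 ÷ 6.25 = 10.2 weeks, which does not fit the planned 7 months, so that case is left out.

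**4. Infants outside the group.** The protocol summary lets enrollment run on into the next, higher dose group without a pause, so infants there could also be dosed before the review. In the 3 days after the last active infant's dose this averages 1.5 × 3/7 = 0.6 active infants at 12 sites, or 1.05 × 3/7 = 0.45 at the slower rate. The SAP (Executive Summary and Section 2.2.1) instead requires SRC approval before escalation, which would prevent this.

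**5. Death after the group's own review.** It waits for the next group's review. Consecutive reviews are 8 ÷ 1.5 = 5.3 weeks apart at 12 sites and 8 ÷ 1.05 = 7.6 weeks at the slower rate. Dosing Group IV is the exception: no group follows it, so no further infants are exposed.

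**The case against.** The strongest defence is that the limit is deliberate. All three statements agree, and the protocol summary takes the hold criteria from Study 03-CL-1201. A 12-hour window suits acute effects of a 30 to 90 minute aerosol, whereas later deaths at 26 to 28 weeks are easily confounded with complications of prematurity. This supports keeping automatic suspension for early deaths. It does not explain why a late death that has been rated related should not bring the committee together.

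The second defence is that oversight continues, and most of it stands. Besides the reporting described above, Section 9.1.5 requires immediate notice to the sponsor of an unanticipated device-associated death, and SAP Section 7.3 requires surveillance of SAEs and deaths at least quarterly. Section 5.2.4 allows a dose reduction after SRC consultation. Under Section 10.3 the SRC may terminate the study for safety, a regulator may request termination, and termination may follow a finding that the drug's risk is significant. None of these is an automatic SRC review. The sponsor's 30-day notice clause and the IRB's site-termination clause in Section 10.3 apply only to reasons other than safety, so they are not safeguards here.

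A reader might infer more than the documents support:

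- That a late related death escapes independent review. It does not: Section 6.1 makes SAE case review part of every scheduled SRC review. The restricted count applies only to an automatic hold.
- That 2 of 8 is an expected outcome. It is what the rule permits.
- That the death in Study 03-CL-1201 nine days after 150 mg/kg shows the rule failing. That death was judged unrelated, so neither the present rule nor the proposed one would respond to it.

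**Conclusion.** The gap is real but narrow: one automatic step is missing, against a background of mandatory reporting and discretionary powers. It is worth closing because the step is cheap and concerns a related death. The upper figures (7 further infants, 5.1 or 7.1 weeks) need the death to be in the group's first active infant and nobody to use discretion; the averages are 3.5 infants and 2.8 or 3.8 weeks. They rest on the accrual assumptions in Section 2.3. The counts cover the same dosing group only, so under the protocol's rule of no pause they are slightly low. The documents give no rate of related death by time since dosing, so no probability of harm is claimed. Section 9.2, Medical Monitoring, was not visible, and anything it adds should be checked.

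**What to change.** In the protocol summary, Protocol Section 6.2 and SAP Section 7.2, add one sentence: any on-study death rated Possibly Related or Related (the Section 9.1.1 categories) to the drug or device, at any time after an initial or repeat dose, calls the unscheduled SRC meeting already described in Section 6.2, and the SRC decides whether enrollment and dosing are suspended. Keep automatic suspension for related deaths within 12 hours, reworded to run from any administration so that repeat doses are covered. Keep the more-than-2 SAE rule. Deaths rated Not related or Unlikely Related would not trigger the meeting.

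The cost is an occasional extra meeting of a committee of 3 to 5, sometimes for a death that is only possibly related. The hold criteria would no longer match Study 03-CL-1201 exactly, and the amendment itself needs IRB approval (Section 15.1). Calling the meeting adds no automatic pause, so the IRB re-approval that follows a hold would arise only if the SRC chose to suspend.
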